### 6. Study Methodology

The proposed study is a prospective, randomized controlled trial (RCT) that aims to compare the effectiveness of two topical treatments, HM Gel (Hydrophilic Methacrylate Gel) and BS Ointment (Beta Sitosterol Ointment), in promoting the healing process of episiotomy and cesarean section scars. The study will include two groups: an experimental group receiving HM Gel and a control group receiving BS Ointment.

**Sample size calculation or justification of numbers:** A priori sample size calculation will be conducted to determine the required number of participants for adequate statistical power. This calculation will consider factors such as the expected effect size, desired level of significance, power of the study, and anticipated dropout rate. We aim to recruit enough participants to ensure the statistical validity and generalizability of the study results.

The sample size for this study was determined based on the desired level of statistical power (80%) and the significance level (0.05). Since no prior estimates of effect size were available, a moderate effect size was assumed. Using a two-sample t-test, the sample size per group was calculated to be 53 participants in patients with cesarean section. Considering rounding up to the nearest whole number, a total sample size of

106 participants was determined for the 2 groups of cesarean section, and the same number for patients (53) with episiotomy, a total of 106 participants was determined for the 2 groups of vaginal delivery with episiotomy. This sample size calculation ensures that the study will have sufficient power to detect meaningful differences in pain levels and wound healing outcomes.

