### Outcomes

- 1- The primary outcome of this trial is to assess the effectiveness of Hydrophilic Methacrylate Gel (Hemagel) in promoting wound healing and reducing complications in patients undergoing episiotomy or cesarean section procedures. Specifically, we aim to compare the rate and quality of wound healing between the group receiving Hemagel Ointment and the control group.
- 2- The secondary outcome includes evaluating the impact of Hydrophilic Methacrylate Gel on pain management, scar appearance, and patient satisfaction. We will assess pain levels using standardized pain scales and compare the effectiveness of Hemagel Ointment in alleviating pain compared to the control group. Additionally, scar appearance will be evaluated using validated assessment tools to determine if Hemagel Ointment leads to improved cosmetic outcomes. Patient satisfaction will be assessed through questionnaires to gauge the subjective experience and level of satisfaction with the treatment.

By achieving these objectives, this trial aims to provide evidence regarding the effectiveness of Hydrophilic Methacrylate Gel in promoting wound healing, managing pain, improving scar appearance, and enhancing patient satisfaction in the context of post-episiotomy and cesarean section scar.

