#### Statistical Analysis Plan:

The statistical analysis plan will be as follows:

- **Descriptive Statistics:**  
Descriptive statistics will be used to summarize the demographic and baseline characteristics of the participants in both groups. Continuous variables, such as age and BMI, will be presented as means with standard deviations or medians with interquartile ranges, depending on their distribution. Categorical variables, such as parity and type of surgery, will be summarized as frequencies and percentages.
- **Primary Outcome Analysis:**  
The primary outcome of wound healing will be analyzed using appropriate statistical methods. As the wound healing outcome is likely to be a categorical variable (e.g., healed/not healed), we will employ the chi-square test or Fisher's exact test, depending on the expected cell frequencies, to compare the proportions of healed wounds.

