## HMC RESEARCH PROTOCOL

between the two treatment groups.

- **Secondary Outcome Analysis:**

For secondary outcomes, such as pain management, scar appearance, and patient satisfaction, we will use similar statistical methods. Pain management and patient satisfaction may be assessed using standardized pain scales and questionnaires, respectively. Depending on the distribution of the data, we will utilize t-tests or Mann-Whitney U tests to compare continuous variables and chi-square tests or Fisher's exact tests for categorical variables.

- **Intention-to-Treat (ITT) Analysis:**

The primary analysis will be conducted on an intention-to-treat (ITT) basis, including all randomized participants. This approach accounts for protocol deviations and maintains the randomization balance between the groups. Participants will be analyzed according to their allocated treatment group, irrespective of protocol adherence or completion.

- **Subgroup Analyses:**

We will perform subgroup analyses to explore potential effect modifiers, such as age, BMI, or parity, on the treatment outcomes. Interaction tests or stratified analyses may be employed to investigate the impact of these factors on the primary and secondary outcomes.

- **Statistical Software:**

All statistical analyses will be performed using a reputable statistical software package, such as SPSS or R. These software tools are widely used for data analysis and will provide reliable results for this study.

- **Statistical Significance:**

Statistical significance will be defined as a p-value less than 0.05. Results with p-values less than this threshold will be considered statistically significant, indicating a significant difference between the treatment groups.

- **Who Will Perform the Analysis:**

The data analysis will be carried out by qualified statisticians [name] (HMC biostatistician) with expertise in statistical methods. These individuals will be independent of the study's clinical team and will be blinded to the treatment allocation to ensure unbiased analysis.

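### Using Fisher's exact test as the fallback for sparse tables gives up some power if nearly all (or nearly no) wounds are healed; Boschloo's test would recover part of it at the cost of one sentence

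*Combined protocol and SAP*

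**What the plan says.** Section 10, Primary Outcome Analysis, treats the form of the outcome as provisional: "As the wound healing outcome is likely to be a categorical variable (e.g., healed/not healed". It then names the chi-square test or Fisher's exact test, "depending on the expected cell frequencies, to compare the proportions of healed wounds". It gives no cut-off for the switch. The Secondary Outcome Analysis paragraph names chi-square or Fisher's "exact tests for categorical variables". On the threshold, the plan says "Statistical significance will be defined as a p-value less than 0.05", without stating sidedness.

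Section 6 sizes each surgery type separately at 53 per group by a two-sample t-test, from "the desired level of statistical power (80%) and the significance level (0.05"; for the difference to be detected, "a moderate effect size was assumed". It then raises recruitment to about 60 per group and anticipates 10% dropout. Section 10 compares the two treatment groups on an intention-to-treat basis and leaves type of surgery to subgroup analyses. No expected healing rate appears anywhere.

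**The concern.** Fisher's test conditions on both margins of the table. When one margin is small, few p-values are attainable and the true error rate can fall well below the nominal 5%. Power is then lost to the choice of test alone. Boschloo's test uses the Fisher p-value as its statistic but calibrates it over the unknown common healing rate. It holds 5% as a stand-alone test and rejects whenever Fisher does.

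The sparse case is possible here. The eligibility criteria remove many women at risk of poor healing, and visits fall at Day 5 and Day 12, so the proportion healed could be near the floor early or near the ceiling late. A real difference between the products could then be reported as not significant where an equally defensible exact test would have found it.

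**Working it through.** **The plan's own figure.** The 53 per group comes from a t-test, so it does not bear directly on a binary test, and there is no binary power figure to reproduce. A standardised difference of 0.5, two-sided, needs 64 per group; 0.55 gives 53. Allowing for dropout, 53/0.90 = 58.9, which fits the target of about 60.

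**Inputs from the documents.** Alpha is 0.05. There are about 60 per arm in each surgery type, or 60 × 0.90 = 54 after dropout. Pooling the two surgery types gives 108 to 120 per arm.

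**Assumptions.** The test is two-sided, the switch occurs when any expected count is below 5, the arms are equal, and about 60 per group means per arm within a surgery type. The healing rates are illustrative.

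**When the fallback applies.** With equal arms, the smallest expected count is half the smaller of total healed and total unhealed. It is below 5 when that total is below 10. With 54 per arm, fewer than 10 of 108 means more than 98/108 = 91% healed overall, or less than about 9%. With 108 per arm, it means more than 206/216 = 95% healed.

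**Method.** All 2x2 tables were enumerated under two independent binomials, and the probabilities of the rejecting tables were summed. The stated rule is uncorrected chi-square, with Fisher in sparse tables. The alternative changes only the sparse branch: it rejects if the Fisher p-value is at or below the largest cut-off that keeps the size of the stand-alone test within 5% (0.074 at 54 per arm, 0.066 at 60 and 108, 0.065 at 120).

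**A table to check by hand.** Suppose 54/54 heal on one product and 49/54 on the other. Fisher's p = 2 × C(54,5)/C(108,5) = 2 × 0.0284 = 0.057, so the stated rule does not reject. Since 0.057 is below 0.074, Boschloo does.

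**True type I error of the stated rule**

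| Per arm | 90% healed | 95% healed | 97% healed |
|---|---|---|---|
| 54 | 4.2% | 1.1% | 0.2% |
| 60 | 4.6% | 1.5% | 0.3% |
| 120 | 5.2% | 4.3% | 1.9% |

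At 54 per arm, the Boschloo fallback brings the 95% and 97% figures only to 2.6% and 1.0%. Chi-square alone is at 3.1% at 97% healed.

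**Power (%), stated rule → Boschloo fallback**

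| Healed | 54 per arm | 60 per arm | 108 per arm | 120 per arm |
|---|---|---|---|---|
| 99 v 90 | 33.4 → 47.9 | 41.6 → 55.5 | 84.8 → 88.0 | 90.0 → 90.3 |
| 99 v 88 | 50.3 → 63.9 | 59.5 → 71.3 | 94.4 → 95.5 | 96.8 → 96.9 |
| 98 v 85 | 63.1 → 71.3 | 71.5 → 77.5 | 96.4 → 96.5 | 97.9 → 97.9 |
| 97 v 83 | 67.4 → 72.1 | 74.6 → 77.5 | 96.0 → 96.0 | 97.5 → 97.5 |
| 95 v 85 | 38.3 → 41.4 | 43.8 → 45.8 | no gain | no gain |
| 95 v 80 | 67.1 → 68.4 | 72.4 → 73.0 | no gain | no gain |
| 90 v 70 | 76.3 → 76.3 | 80.2 → 80.2 | no gain | no gain |

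For small differences near the ceiling in a pooled test, 99 v 94 gives 38.2 → 48.7 at 108 per arm and 45.8 → 49.4 at 120. For 99 v 92 the figures are 65.9 → 72.9 and 73.7 → 75.0.

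**Worst case.** The maximum type I error over all common healing rates is 5.2% to 5.5% across these sizes. It is essentially the same for both procedures, because it arises in the chi-square branch that both share.

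**The case against.** The strongest reply is that chi-square with Fisher for small expected counts is a conventional, prespecified rule that does not inflate false positives, so replacing it is a preference. That stands: nothing here is an error in the plan.

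Second, the size of the loss depends on rates that the documents do not give. A reader might infer from the 54-per-arm column that the trial forfeits 5 to 15 points of power. The documents do not support that. Every larger loss needs one arm at 97% to 99% healed, and the written primary comparison reads as pooled, where the same contrasts lose 0 to 3 points. A per-surgery test remains possible, because section 6 sizes each surgery type separately.

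Third, the low error rate in sparse tables is partly due to the data and not to Fisher, since chi-square also falls below 5% there. This too stands, and Boschloo narrows the gap without closing it.

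Fourth, the form, timing and expected rate of the endpoint are still open, and these are larger questions. They limit the priority of this point, but a better fallback costs the same whichever way they are settled.

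**Conclusion.** The point holds as a conditional loss of efficiency. If each surgery type is analysed separately with 54 to 60 per arm and healing is near the ceiling, the Fisher fallback gives up about 3 to 15 points of power against Boschloo. At 95% v 80% to 85% it gives up about 1 to 3 points, and at 90% v 70% nothing. Pooled, the loss is 0 to 3 points for the same contrasts and about 1 to 11 points for 99% v 92% to 94%. By symmetry, the same holds near the floor. All of this rests on an assumed cut-off of 5, a two-sided test and assumed healing rates.

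Two stronger readings should be avoided. One is that the change restores a 5% error rate in sparse tables; it does not. The other is that the figures carry over to complications. The Outcomes section includes them in the primary outcome ("promoting wound healing and reducing complications in patients undergoing episiotomy or cesarean section procedures"), but the primary analysis paragraph names a test only for healed wounds, so there is no specified complication test to criticise.

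Priority: optional refinement.

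**What to change.** In section 10, under Primary Outcome Analysis and Secondary Outcome Analysis:

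- State the expected-count cut-off at which the test switches.
- For 2x2 tables, name Boschloo's unconditional exact test in place of Fisher's as the fallback.
- Report the difference in proportions with a score-based 95% confidence interval beside the p-value.

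The cost is about one sentence in each place, with no new data or participants. Boschloo's test may need R, which the Statistical Software paragraph already allows. At the sizes checked, the change never lowered power and left the maximum type I error essentially where it is.

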## HMC RESEARCH PROTOCOL

between the two treatment groups.

- **Secondary Outcome Analysis:**

For secondary outcomes, such as pain management, scar appearance, and patient satisfaction, we will use similar statistical methods. Pain management and patient satisfaction may be assessed using standardized pain scales and questionnaires, respectively. Depending on the distribution of the data, we will utilize t-tests or Mann-Whitney U tests to compare continuous variables and chi-square tests or Fisher's exact tests for categorical variables.

- **Intention-to-Treat (ITT) Analysis:**

The primary analysis will be conducted on an intention-to-treat (ITT) basis, including all randomized participants. This approach accounts for protocol deviations and maintains the randomization balance between the groups. Participants will be analyzed according to their allocated treatment group, irrespective of protocol adherence or completion.

- **Subgroup Analyses:**

We will perform subgroup analyses to explore potential effect modifiers, such as age, BMI, or parity, on the treatment outcomes. Interaction tests or stratified analyses may be employed to investigate the impact of these factors on the primary and secondary outcomes.

- **Statistical Software:**

All statistical analyses will be performed using a reputable statistical software package, such as SPSS or R. These software tools are widely used for data analysis and will provide reliable results for this study.

- **Statistical Significance:**

Statistical significance will be defined as a p-value less than 0.05. Results with p-values less than this threshold will be considered statistically significant, indicating a significant difference between the treatment groups.

- **Who Will Perform the Analysis:**

The data analysis will be carried out by qualified statisticians [name] (HMC biostatistician) with expertise in statistical methods. These individuals will be independent of the study's clinical team and will be blinded to the treatment allocation to ensure unbiased analysis.

## HMC RESEARCH PROTOCOL

### 11. Adverse Event Reporting

#### Monitoring and Reporting of Adverse Events:

We will implement a systematic monitoring and reporting process to promptly identify and assess adverse events throughout the study. The following steps will be followed:

-Participant Education: Participants will be provided with clear instructions on how to recognize and report any potential adverse events they may experience during the study. They will be informed about the importance of timely reporting and the methods for contacting the study team.

-Documentation: All adverse events reported by the participants or observed by the study personnel will be documented in detail. This documentation will include the nature of the event, date and time of occurrence, severity, duration, related symptoms, and any actions taken.

-Classification and Severity Assessment: Adverse events will be classified and assessed for severity according to predefined criteria. The severity levels may include mild, moderate, or severe, based on the impact on the participant's well-being and the need for medical intervention.

-Causality Assessment: Adverse events will be evaluated for their potential relationship to the investigational product (Hemagel Ointment) or other study procedures. Causality assessments will consider factors such as temporal association, known side effects of the product, and the presence of alternative explanations.

-Reporting and Follow-up: Adverse events of moderate to severe intensity or those considered related to the investigational product will be promptly reported to the principal investigator and the relevant ethics committee or institutional review board (IRB). The reporting will include a comprehensive description of the event, its severity, the participant's characteristics, and any actions taken or planned.

We will ensure that the reporting timelines align with the revised version of IRB SOP 09, available on the Abhath download center. Specifically, Serious Adverse Events (SAE) will be reported within 7 days, and any other unanticipated problems will be reported within 14 days.

We are committed to ensuring the highest standards of participant safety and ethical conduct throughout the study.

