## HMC RESEARCH PROTOCOL

Additionally, its mechanism of action involves the formation of a protective barrier over the wound site, potentially reducing infection risk and facilitating a controlled healing process (8).

While some studies have explored the application of Hemagel Ointment in wound healing, its specific effects on post-episiotomy and CS scars remain relatively uncharted territory. Consequently, there exists a compelling need to conduct well-designed clinical trials that rigorously assess Hemagel Ointment's efficacy and safety in the context of these surgical procedures.

Therefore, the aim of this study is to evaluate the effectiveness and safety of Hemagel Ointment in post-episiotomy and cesarean section scar care through a randomized clinical trial. This trial will provide comprehensive evidence regarding the effectiveness of Hemagel Ointment in promoting wound healing, alleviating pain, improving scar appearance, and enhancing patient satisfaction in these specific contexts.

By conducting a rigorous randomized clinical trial, we seek to generate high-quality data that will inform clinical practice and guide healthcare professionals in selecting optimal interventions for scar management in post-episiotomy and cesarean section cases. This research will contribute to the existing body of knowledge in scar care and provide valuable insights for healthcare professionals, ultimately improving patient outcomes.

The results of this study have the potential to facilitate evidence-based decision-making, facilitate personalized patient care, and potentially reduce the burden of complications associated with post-episiotomy and cesarean section scars. Furthermore, the findings will contribute to advancing the field of scar management and may pave the way for future research and the development of targeted interventions.

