### 4. Objectives

- 1- The primary objective of this trial is to evaluate the effectiveness of Hemagel Ointment in promoting wound healing and reducing complications among patients who have undergone episiotomy or cesarean section procedures. The assessment of wound healing will be conducted using a validated assessment tool, which is included as an attachment.
- 2- The secondary objectives of this study involve assessing the impact of Hemagel Ointment on pain management, scar appearance, and patient satisfaction. To measure pain levels, standardized pain scales will be utilized, allowing for a

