### Follow-Up Phone Calls:

Phone call reminders will be made by trained staff to assess treatment adherence. Specific timepoints for planned follow-up phone calls are Day 3 and Day 7.

These follow-up calls will serve to reinforce proper application, address any concerns, and ensure consistent adherence to the treatment regimen. The detailed script in the ABHATH documentation provides guidance for the phone call reminders.

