### Data Collection:

Data collection will involve objective measures and participant-reported outcomes. The assessment will include wound healing progress, scar appearance, pain levels, and patient satisfaction. These parameters will be assessed at predetermined intervals using standardized assessment tools and scoring systems.

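### Complications are part of the primary objective and outcome, and safety is in the aim, but neither is defined, named in the data lists or compared between arms in the analysis plan

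*Combined protocol and SAP*

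**What the plan says.** **Aims.** Section 3 (Introduction / Background) says that "the aim of this study is to evaluate the effectiveness and safety of Hemagel Ointment in post-episiotomy and cesarean section scar care". Section 4 (Objectives) gives the primary objective as effectiveness in "promoting wound healing and reducing complications among patients who have undergone episiotomy or cesarean section procedures". The Outcomes section repeats this for the primary outcome: "in promoting wound healing and reducing complications in patients undergoing episiotomy or cesarean section procedures". The Risk section names allergic reaction, skin irritation, delayed healing, unsatisfactory scar appearance, lack of effect and infection. No section says which events count as complications.

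**Data.** Section 6, on the data collected at each time point, lists wound healing, scar appearance, pain and satisfaction. Data Collection in section 7 repeats the four: "The assessment will include wound healing progress, scar appearance, pain levels, and patient satisfaction".

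**Contacts.** Visits are at recruitment, Day 5 and Day 12, and calls are on Day 3 and Day 7. The purpose given for the calls is adherence: "Phone call reminders will be made by trained staff to assess treatment adherence". The same section adds that they will deal with concerns.

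**Capture of events.** Section 11 announces a systematic process. Its steps are participant education, documentation, grading, causality assessment, reporting and follow-up. On documentation it says "All adverse events reported by the participants or observed by the study personnel will be documented in detail".

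**Analysis.** The primary analysis in section 10 compares the proportions of healed wounds. For the rest it says: "For secondary outcomes, such as pain management, scar appearance, and patient satisfaction, we will use similar statistical methods". No analysis of complications or adverse events is named.

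**The concern.** One component of the stated primary outcome has no definition, no named data item and no planned comparison. A team that follows the written plan will have an event log and a test of healed against not healed. Any later statement that the gel reduces complications, or is as safe as the control ointment, would need an event definition and an analysis chosen after the data exist.

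Capture matters as well. Itching, a passing rash or irritation can come and go between the Day 5 and Day 12 visits. Under the listed steps such an event reaches the log only if the woman raises it. What is not asked during follow-up cannot be reliably recovered afterwards.

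**Working it through.** The plan gives no complication rate, adverse event rate or safety sample size, so there is no figure to reproduce. The check is first a comparison of sections, then an illustration of what the planned numbers could show.

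**Step 1. Sections side by side**

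| Item | Aim, objective or outcome | Data lists (sections 6 and 7) | Analysis (section 10) |
|---|---|---|---|
| Wound healing | Primary | Named | Healed / not healed, chi-square or Fisher |
| Complications | Primary | Not named | None named |
| Pain, scar appearance, satisfaction | Secondary | Named | t-test, Mann-Whitney, chi-square or Fisher |
| Safety / adverse events | Aim in section 3 | Not named | None named |

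Delayed healing is partly covered by healed / not healed. Skin reactions are not: a woman with a rash whose wound closes counts as healed. Infection is covered only so far as it prevents healing.

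**Step 2. Is a question scheduled for every woman?** None of the steps in section 11 contains one. The note under Exclusion Criteria in section 7 shows the contrast: there, providers must actively ask about changes in medication or supplements at follow-up visits. Nothing similar is written for adverse events.

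**Step 3. Numbers available.** The Sample Size Adjustment paragraph gives about 60 per group. The calculation before it is made separately for cesarean section and episiotomy. I therefore take 60 per arm within each surgery type, and 2 × 60 = 120 per arm pooled. With the anticipated 10% dropout, these become 60 × 0.9 = 54 and 120 × 0.9 = 108.

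**Step 4. Zero events.** The exact one-sided 95% upper bound is 1 − 0.05^(1/n).

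- n = 120: 1 − 0.05^(1/120) = 2.5%
- n = 108: 1 − 0.05^(1/108) = 2.7%
- n = 60: 1 − 0.05^(1/60) = 4.9%
- n = 54: 1 − 0.05^(1/54) = 5.4%

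These bounds assume that every event is captured.

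**Step 5. Comparison at assumed rates of 10% and 5%** (two-sided 5% level, normal approximation).

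- Pooled rate 0.075. At 120 per arm, the standard error under no difference is √(2 × 0.075 × 0.925 / 120) = 0.0340.
- Standard error under the assumed rates: √(0.10 × 0.90 / 120 + 0.05 × 0.95 / 120) = 0.0339.
- Power = Φ((0.05 − 1.96 × 0.0340) / 0.0339) = Φ(−0.49) = 31%.
- The same formula gives 18% at 60 per arm. Power of 80% would need 435 per arm.
- Half-width of the 95% interval for the risk difference: 1.96 × 0.0339 = 6.6 points at 120 per arm. At 60 it is 1.96 × √(0.09/60 + 0.0475/60) = 9.4 points.

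**Step 6. Incomplete capture (assumed).** If only half of the events were recorded in each arm, 10% and 5% would appear as 5% and 2.5%. Power at 120 per arm would fall from 31% to 17%.

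**The case against.** **The forms are unseen.** Data follow an attached collection sheet, healing is scored with an attached tool, and calls follow a script held elsewhere. Any of these could contain infection, irritation or adverse event items. The data lists are also introduced by open wording. This stands, and it rules out saying that complications are not collected. It does not supply an analysis: even if the forms hold such items, section 10 names no comparison of them.

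**Monitoring is promised, and staff see the wounds.** Section 11 commits to a systematic process and to following events until they resolve or stabilise. Wounds are assessed at scheduled visits, and the calls invite concerns. A reader might infer that events are logged only by luck; that goes too far. What stands is that no question to every woman is specified.

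**Safety is an aim in the background only.** The formal objectives and outcomes do not list it, and no safety conclusion is announced. A reader might infer that the trial cannot support its safety conclusion, but the documents contain no such conclusion to refute. Complications, however, are in the formal objective and outcome.

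**Unequal reporting between arms is speculative.** A reader might infer a biased comparison because women could report differently on a new product and a familiar one. The protocol plans blinded tubes in identical outer packaging, and nothing in the documents supports any particular gap in reporting. I do not rely on it.

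**Sample size is itself a limit.** This is correct. With complete capture, 31% power at 10% against 5% would still be poor. A checklist improves the record; it does not make this a powered safety trial.

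**Conclusion.** The concern holds in this form: complications are part of the primary objective and outcome and safety is in the aim, yet complications are undefined, unnamed in the protocol's data lists and without a between-arm analysis. The written steps for adverse events contain no scheduled question. As written, the plan gives no prespecified basis for a comparative statement on complications or safety.

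The mismatch between sections rests on the text alone. The zero-event bounds of about 2.5% (120 per arm) and 4.9% (60 per arm within one surgery type) assume complete capture and no dropout; with 10% dropout they are 2.7% and 5.4%. The 31% power rests on assumed rates of 10% and 5%, which the documents do not give. The added comparison should therefore be presented as descriptive. This should be corrected, but it does not undermine the healing comparison.

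**What to change.** 1. **Define complications** from the risks already named in the Risk section: allergic reaction (rash, itching, swelling), irritation at the site, wound infection, and delayed closure or wound opening. Add them to the data lists in sections 6 and 7.
2. **Ask every woman in both arms the same fixed checklist** at the existing Day 3 and Day 7 calls and Day 5 and Day 12 visits, kept apart from the adherence questions. If the attached sheet, wound tool or call script already does this, say so in section 11 and refer to it.
3. **Add a table to section 10**, by arm, overall and by surgery type, with the number and percentage of women with each complication and with any adverse event, the risk difference and its 95% confidence interval. State that it is descriptive and that precision is limited, and word any statement on safety or complications on the interval, not on the absence of a significant difference.

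The cost is a few minutes per contact, about a page on the data sheet and script, and one table. Recorded event rates will be higher in both arms than under participant reports and staff observation alone, and the report should explain why.
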